6.6 Additional treatment guidance

6.6.1 Treatment compliance

Compliance will be ensured by the investigator and/or study personnel at each dosing visit. This information should be captured in the source document at each visit. Study drug (inclisiran) accountability will also be determined by the site monitor while performing routine site visits and at the completion of the study.

Duration of study drug exposure will be calculated based upon the dates recorded in the eCRF.

6.7 Preparation and dispensation

Each study site will be supplied with study drug in packaging as described under investigational and control drugs section (Section 6.1.1).

A unique medication number is printed on the study medication label.

Investigator staff will identify the study medication kits to dispense to the participant by contacting the IRT and obtaining the medication number(s). The study medication has a 2-part label (base plus tear-off label), immediately before dispensing the medication kit to the participant, site personnel will detach the outer part of the label from the packaging and affix it to the source document.

All kits of study treatment assigned by the IRT will be recorded in the IRT system.

As per Section 4.6, during a Public Health emergency that limits or prevents on-site study visits, a home health nurse is permitted to administer the study medication at a participant's home (if allowed by Local or Regional Health Authorities and Ethics Committees as appropriate) in the event the Investigator has decided that an on-site visit by the participant is no longer appropriate or possible. The dispatch of study medication from the site to the participant's home remains under the accountability of the Investigator.

6.7.1 Handling of study treatment and additional treatment

6.7.1.1 Handling of study treatment

Study treatment must be received by a designated person at the study site, handled and stored safely and properly and kept in a secured location to which only the investigator and designated site personnel have access. Upon receipt, all study treatment must be stored according to the instructions specified on the labels.

Clinical supplies are to be dispensed only in accordance with the protocol. Technical complaints are to be reported to the respective Novartis US Quality Assurance representative.

Medication labels will include storage conditions for the study treatment but no information about the participant except for the medication number.

The investigator must maintain an accurate record of the shipment and dispensing of study treatment in a drug accountability log. Monitoring of drug accountability will be performed by monitors during site visits or remotely and at the completion of the trial.

At the conclusion of the study, and as appropriate during the course of the study, the investigator will return all unused study treatment, packaging, drug labels, and a copy of the completed drug accountability log to the Novartis monitor or to the Novartis address provided in the investigator folder at each site.

6.7.2 Instruction for prescribing and taking study treatment

Packaging and Labeling

Investigational product [Inclisiran (KJX839), 284 mg Liquid PFS, 1.5 ml] will be provided by the sponsor. Medication labels will comply with regulatory requirements. The storage conditions will be described on the medication label.

The container closure system for the prefilled syringe consists of a Type I glass syringe with a stainless steel 27G 1/2" staked needle covered by a removable rigid needle shield and Flurotech covered bromobutyl plunger.

Table 6-4 Dose and treatment schedule

Investigational / Control Drug (Name and Strength)	Dose	Frequency and/or Regimen	
Inclisiran (KJX839), 284 mg Liquid in PFS, 1.5 mL	Inclisiran sodium 300 mg/1.5 mL (equivalent to 284 mg inclisiran), s.c. use	Initially, 90 days later, 180 days after the second dose	

Participants will be administered a single SC injection of 300 mg Inclisiran sodium for injection at predefined time points as described in the Schedule of Assessments (Table 8-1). Investigational product injection will be administered by qualified clinical study site staff under the supervision of the investigator or designee. The site of injection is the abdomen, arm or thigh. Do not inject into areas of active skin disease or injury such as sunburns, skin rashes, inflammation, tattoos or skin infections.

All kits of study treatment assigned by the IRT will be recorded in the IRT system.

7 Informed consent procedures

Eligible participants may only be included in the study after providing (witnessed, where required by law or regulation), IRB/IEC-approved informed consent.

If applicable, in cases where the participant's representative(s) gives consent (if allowed according to local requirements), the participant must be informed about the study to the extent possible given his/her understanding. If the participant is capable of doing so, he/she must indicate agreement by personally signing and dating the written informed consent document.

Informed consent must be obtained before conducting any study-specific procedures (e.g., all of the procedures described in the protocol). The process of obtaining informed consent must be documented in the participant source documents.

Novartis will provide to investigators in a separate document a proposed informed consent form that complies with the ICH GCP guidelines and regulatory requirements and is considered appropriate for this study. Any changes to the proposed consent form suggested by the investigator must be agreed by Novartis before submission to the IRB/IEC.

Information about common side effects already known about the investigational drug can be found in the Investigator's Brochure (IB). This information will be included in the participant informed consent and should be discussed with the participant during the study as needed. Any new information regarding the safety profile of the investigational drug that is identified between IB updates will be communicated as appropriate, for example, via an investigator notification or an aggregate safety finding. New information might require an update to the informed consent and then must be discussed with the participant.

The following informed consents are included in this study:

• Main study consent, which also includes:

- As applicable, the consent will include language for the use of de-identification and tokenization technology that will allow for the acquisition and linkage of the participant to their health care data that exists in pharmacy and medical administrative claims databases
- · As applicable, Pregnancy Outcomes Reporting Consent for female participants

Women of childbearing potential must be informed that taking the study treatment may involve unknown risks to the fetus if pregnancy were to occur during the study and agree that in order to participate in the study they must adhere to the contraception requirements.

A copy of the approved version of all consent forms must be provided to Novartis after IRB/IEC approval.

Participants might be asked to complete an optional questionnaire to provide feedback on their clinical trial experience.

8 Visit schedule and assessments

The Assessment Schedule (Table 8-1) lists all assessments when they are performed. All data obtained from these assessments must be supported in the participant's source documentation.

Participants should be seen for all visits/assessments as outlined in the assessment schedule (Table 8-1) or as close to the designated day/time as possible (+/- 7 days). Missed or rescheduled visits should not lead to automatic discontinuation.

Participants who discontinue from study treatment should continue to attend the remaining study visits as indicated in the Assessment Schedule (Table 8-1).

Participants who discontinue from study or withdraw their consent should be scheduled for a final evaluation visit if they agree, as soon as possible, at which time all of the assessments listed for the final visit will be performed. At this final visit, all investigational product should be reconciled, and the adverse event and concomitant medications not previously reported must be recorded on the eCRF.

Participants will have to comply with the following restrictions during the study:

- Participants need to fast for at least 8 hours for all visits (measurement of lipids/lipoproteins and blood glucose requires participants to be fasting). If the participant has not fasted, the collection of laboratory evaluations must be rescheduled.
- Blood donation will not be allowed at any time during the study

The "X" in the table denotes the assessments to be recorded in the clinical database or received electronically from a vendor. The "S" in the table denotes the assessments that are only in the participant's source documentation and do not need to be recorded in the clinical database.

As per Section 4.6, during a Public Health emergency that limits or prevents on-site study visits, alternative methods of providing continuing care may be implemented by the investigator as the situation dictates. If allowable by a local Health Authority and depending on operational capabilities, phone calls, virtual contacts (e.g. tele consult) or visits by site staff/ home nursing staff to the participant's home, can replace on-site study visits, for the duration of the disruption until it is safe for the participant to visit the site again.

If a public health emergency limits or prevents on-site study visits, alternative methods of providing continuing care may be implemented. Virtual visits [e.g., phone calls, video visits (preferred)] or visits by site staff/home nursing service to the participant's home depending on local regulations and capabilities, can replace on-site study visits, for the duration of a public health emergency until it is safe for the participant to visit the site again.

Unscheduled Visits

Participants may be seen at any time for an unscheduled visit, e.g., if they experience deterioration or AEs that in the opinion of the Investigator/qualified site staff requires closer monitoring. The assessment(s) performed at an unscheduled visit must include at a minimum: an assessment of concomitant medications, vital signs, and an AE/SAE assessment. Any additional assessments performed are at the Investigator/qualified site staff's discretion.

Table 8-1 Assessment Schedule

Period	Screening	Treatment ¹			Unplanned	
Visit Name	Visit 1	Baseline/Visit 2	Visit 3	Visit 4	EOS/Visit 5	Unscheduled Visit
Days	-30 to -1	0	90	270	330	-
Informed Consent	Х					
Inclusion / Exclusion criteria	Х	X				
Physical Examination	S		S	S	S	
Demography	Χ					
Medical History	Χ					
ACS Medical History	Χ					
Statin Intolerance Medical History	X					
Height and Weight ²	Χ	X	X	X	Χ	
Pulse Rate	X	X	X	X	Χ	X
Blood Pressure	Χ	X	Х	Х	X	X
Prior/Concomitant medications ³	Х	X	X	Х	Х	Х
Surgical / Medical procedures	Х	Х	Х	Х	Х	Х
Urinalysis		X			Χ	
Pregnancy and assessments of fertility ⁴	Х	х	х	Х	Х	
Hematology	Х	Х			Х	
Full Clinical Chemistry		Х				
Limited Chemical Chemistry	Х		X	Х	Х	
Hepatitis Markers	Х					
Lipids and lipoproteins ⁵	Х	Х	Х	Х	Х	
Coagulation	Х	Х				
Biomarker-Lipoprotein(a)		Х	Х	Х	Х	

Period	Screening	Treatment ¹			Unplanned	
Visit Name	Visit 1	Baseline/Visit 2	Visit 3	Visit 4	EOS/Visit 5	Unscheduled Visit
Days	-30 to -1	0	90	270	330	-
Electrocardiogram (ECG)	Х					
Randomization		X				
Inclisiran Dose Administration		X	Х	Х		
IRT Transaction	Х	X	Х	Х	X	
Injection Site Reaction Assessment		X	Х	Х	X	
Clinical Outcome Assessment(s)		Х	X	Х	X	
Adverse Events	X	X	X	Х	X	Х

XAssessment to be recorded in the clinical database or received electronically from a vendor

SAssessment to be recorded in the source documentation only

¹Due to a Public Health Emergency, if participant is unable to attend in-person visit, phone or virtual visit is an acceptable alternative. At home visits by site staff or a nursing service may be used to assist with blood draws and/or study medication administration if required at this visit.

²Height only to be performed at Visits 1 and 2

³ 30 days prior to randomization

⁴All female participants of childbearing potential will have a serum pregnancy test (hCG) performed at Visit 1 (central lab). A urine pregnancy test will be conducted at the local site for remaining visits.

⁵LDL-C, apolipoprotein B, VLDL, non-HDL-C, total cholesterol, triglycerides, and HDL-C. In addition, samples will be collected for biobanking at Visits 2-5.

8.1 Screening

A participant's eligibility for the study will be assessed during the 30 day screening period (Day -30 to Day -1). Screening is flexible in duration based on the time required for participants to be evaluated for eligibility. It is permissible to re-screen a participant if s/he fails the initial screening; however, each case must be discussed and agreed with the Sponsor on a case-by-case basis.

8.1.1 Information to be collected on screening failures

Participants who sign an informed consent form and subsequently found to be ineligible will be considered a screen failure. It is permissible to re-screen a participant if he/she fails the initial screening; however, each case must be discussed and agreed with the Sponsor on a case-by-case basis. If the re-screen is approved, a new participant number will be allocated to the participant and he/she will need to re-perform all Visit 1 procedures. A participant may be rescreened once. The participant must provide new written informed consent before they are rescreened.

The reason for screen failure should be entered on the applicable Case Report Form. The demographic information, informed consent, and Inclusion/Exclusion pages must also be completed for screen failure participants. No other data will be entered into the clinical database for participants who are screen failures, unless the participant experienced a serious adverse event during the screening phase (see SAE section for reporting details). If the participant fails to be randomized, the IRT must be notified within 2 days of the screen failure that the participant was not randomized.

Participants who are randomized and fail to start treatment (e.g., participants randomized in error) will be considered an early terminator. The reason for early termination should be recorded on the appropriate Case Report Form.

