Patient-Reported Outcome (PRO)	A measurement based on a report that comes directly from the patient about the status of a participant's health condition without amendment or interpretation of the patient's report by a clinician or anyone else
Period	The subdivisions of the trial design (e.g., Screening, Treatment, Follow-up) which are described in the Protocol. Periods define the study phases and will be used in clinical trial database setup and eventually in analysis
Personal data	Participant information collected by the Investigator that is coded and transferred to Novartis for the purpose of the clinical trial. This data includes participant identifier information, study information and biological samples.
Premature participant withdrawal	Point/time when the participant exits from the study prior to the planned completion of all study drug administration and/or assessments; at this time all study drug administration is discontinued, and no further assessments are planned

Randomization	The process of assigning trial participants to investigational drug or control/comparator drug using an element of chance to determine the assignments in order to reduce bias.
Randomization number	A unique identifier assigned to each randomized participant
Re-screening	If a participant fails the initial screening and is considered as a Screen Failure, he/she can be invited once for a new Screening visit after medical judgment and as specified by the protocol
Remote	Describes any trial activities performed at a location that is not the investigative site where the investigator will conduct the trial, but is for example a home or another appropriate location
Screen Failure	A participant who did not meet one or more criteria that were required for participation in the study
Source Data/Document	Source data refers to the initial record, document, or primary location from where data comes. The data source can be a database, a dataset, a spreadsheet, or even hard-coded data, such as paper or eSource
Start of the clinical trial	The start of the clinical trial is defined as the signature of the informed consent by the first participant
Study treatment	Any drug or combination of drugs or intervention administered to the study participants as part of the required study procedures; includes investigational drug(s), control(s) or background therapy

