The investigator must give the monitor access to all relevant source documents to confirm their consistency with the data capture and/or data entry. Novartis monitoring standards require full verification for the presence of informed consent, adherence to the inclusion/exclusion criteria, documentation of SAEs, and of data that will be used for all primary variables. Additional checks of the consistency of the source data with the CRFs are performed according to the study-specific monitoring plan. No information in source documents about the identity of the participants will be disclosed.

12 Data analysis and statistical methods

Any data analysis carried out independently by the investigator should be submitted to Novartis before publication or presentation.

The analysis will be performed at the end of the trial, after the data for all participants are available.

Unless otherwise specified, all statistical tests will be conducted against a two-sided alternative hypothesis, employing a significance level of 0.05.

Efficacy, safety, and other data will be summarized. For continuous variables, summary statistics (mean, standard deviation, median, 25th and 75th percentiles, interquartile range, minimum, and maximum) at each time point and for change from baseline to each time point will be reported by treatment group. For discrete variables, frequency counts and percentages at each time point will be reported by treatment group.

12.1 **Analysis sets**

The Full Analysis Set (FAS) comprises all randomized participants. According to the intent-totreat principle, participants will be analyzed according to the treatment group they have been assigned to during the randomization procedure.

The Per-Protocol Set is a subset of the Full Analysis Set in which participants are not treated with any inclisiran if they are randomized to the usual care treatment group or do not have any major protocol deviations (including deviations from inclusion/exclusion criteria) in either treatment group.

The Restricted Set 1 is a subset of the Full Analysis Set which includes only participants without changes in background lipid-lowering therapy.

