2.1.1 General definitions

Study treatment

The following are the investigational treatments:

- Inclisiran (KJX839), 284 mg, 1.5 ml liquid in a single-use prefilled syringe (PFS) for s.c. administration plus usual care
- Usual care alone

The following treatment labels will be used for all tables, listings and figures:

- Inclisiran + Usual Care
- Usual Care

Study treatment start and end date

Study treatment start date is defined as the first date when a non-zero dose of study drug is administered for the inclisiran + usual care group. If a participant, who is randomized to the inclisiran + usual care group, does not take any study drug then treatment start date will be the randomization date.

For the usual care alone group the study treatment start date will be the randomization date.

“Day 1” will be used to identify study treatment start date for both treatments.

Study treatment end date is defined as the treatment phase completion date recorded on the “Treatment Disposition” CRF for inclisiran + usual care participants. For the usual care alone group, the study treatment end date is the last recorded contact/participation date in the database.

Study start and end date

Study start date is defined as the first date when a non-zero dose of study drug is administered for the inclisiran + usual care group. If a participant, who is randomized to the inclisiran + usual care group, does not take any study drug then study start date will be the randomization date.

For the usual care alone group the study start date will be the randomization date.

Study end date is defined as the date of last recorded contact/participation date in the database.

Duration of exposure to inclisiran

For the inclisiran + usual care group, duration of exposure to inclisiran (in days) is defined as the number of days from Day 1 to the study *treatment* end date. Duration of exposure will not be defined for the usual care alone group.

Planned and actual treatment definitions

The following definitions will be used for planned and actual treatment.

Table 2-1 Planned and Actual Treatment Definitions

Randomized Treatment Group	Inclisiran Use Scenario During Study (Inclisiran Use Recorded as Study Treatment or Concomitant Medication)	Planned Treatment	Actual Treatment
Inclisiran + Usual Care	Received at least one dose of inclisiran	Inclisiran + Usual Care	Inclisiran + Usual Care
Inclisiran + Usual Care	Never received inclisiran	Inclisiran + Usual Care	Usual Care

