Data collected at scheduled or unscheduled visits will be used in the analysis if they fall into an analysis window for an analysis visit. If more than one visit (scheduled or unscheduled) is made within the window specified above for any analysis visit, the non-missing assessment closest to the target study day will be used in the analysis for that visit. In the case of tied visits, non-missing data from the later visit will be used. In the case of identical collection dates and times, the average of the two visits will be used. However, all data will be included in the participant data listings.

Last Visit Summaries

The protocol uses the term End of Study (EOS) for Day 330. If a participant discontinues from the study early, they will have an early termination visit that is before Day 330. Using the windowing provided in [Table 2-2](#), the early termination visit will be assigned to the nearest analysis visit. Tables that summarize data by visit will include data by analysis visit (Baseline, Day 90, Day 270, and Day 330) along with a Day 330/Last Visit which will combine data from Day 330 for those participants who have data collected within the Day 330 analysis window with the data from the last post-baseline visit for those participants who do not have data collected in the Day 330 analysis window.

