2.5.4 Handling of missing values not related to intercurrent event

For the primary analysis of primary efficacy variable 1, the MMRM implicitly imputes missing data under a missing at random assumption.

For the primary analysis of primary efficacy variable 2, participants with missing LDL-C data will be assumed to have LDL-C \geq 70 mg/dL (i.e., “non-responder”).

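### Protocol 8.1.1 labels randomized participants who never start treatment as early terminators, which is likely to end their follow-up, mainly in the inclisiran arm, although the analysis set keeps them

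*Protocol*

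**What the plan says.** **The rule.** Protocol 8.1.1, in the text on screening failures, says: "Participants who are randomized and fail to start treatment (e.g., participants randomized in error) will be considered an early terminator". It then asks only that the reason be recorded. It neither defines the term nor mentions later visits.

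**How the term is used elsewhere.** SAP 2.1.1 (Last Visit Summaries) says: "If a participant discontinues from the study early, they will have an early termination visit that is before Day 330". SAP 2.6.1, under secondary variable 23, sets early-termination participants apart from study completers and counts them all as having discontinued their statin. The protocol glossary says of premature withdrawal that "at this time all study drug administration is discontinued, and no further assessments are planned".

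**When treatment starts.** SAP 2.1.1: "For the usual care alone group the study treatment start date will be the randomization date". For someone assigned to inclisiran who "does not take any study drug then treatment start date will be the randomization date", the SAP supplies a start date, and SAP Table 2-1 has a row for such participants.

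**Who is analyzed and followed.** Protocol 12.1: "The Full Analysis Set (FAS) comprises all randomized participants", analyzed as assigned. Protocol Section 8: "Participants who discontinue from study treatment should continue to attend the remaining study visits". Protocol 9.1.1 adds that those who stop treatment, or no longer wish to take part, are not withdrawn unless they withdraw consent.

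**Missing data.** SAP 2.5.4 handles variable 1 by MMRM under missing at random. For variable 2, "participants with missing LDL-C data will be assumed to have LDL-C" at or above 70 mg/dL.

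**The concern.** A participant who takes one dose and stops is followed to Day 330. One who takes none is labeled in a way that suggests exit, although both belong to the same analysis set. Allocation is open-label, so a participant can decline the first injection knowing the assignment. Usual care begins at randomization by definition and has no equivalent first step to miss. The resulting loss would occur after randomization, lie mostly in one arm, and be related to acceptance of treatment.

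Three analyses would be affected:

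- **Variable 2:** a never-starter without a Day 330 value becomes a non-responder.
- **Variable 1:** a never-starter with no post-baseline value contributes nothing to the MMRM, so an untreated person leaves the inclisiran mean.
- **Secondary variable 23:** a never-starter classed as an early terminator is counted as having stopped statins, even if still taking one. Participants with a history of statin intolerance are excluded from this analysis.

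**Working it through.** **1. The plan's own figures (Protocol 12.8.1, SAP Section 3).** Inputs: two-sided alpha 0.025, power 0.85, 1:1 allocation, SD 40, difference 15, proportions 0.55 and 0.75, 20% loss to follow-up.

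- Variable 1, per arm: 2 × 40² × (2.2414 + 1.0364)² / 15² = 152.8, rounded up to 153, so 306 in total.
- Variable 2, per arm, pooled variance: [2.2414 × √(2 × 0.65 × 0.35) + 1.0364 × √(0.55 × 0.45 + 0.75 × 0.25)]² / 0.20² = 120.5, rounded up to 121, so 242 in total.
- Loss to follow-up: 153 / 0.8 = 191.25, rounded up to 192 per arm, so 384.

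All three match the documents. The point concerns data collection and does not dispute them.

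**2. Assumptions.** The documents give no never-start rate. Let k of 192 inclisiran participants never start, with k from 0 to 10 (10/192 = 5.2%). Zero is included because randomization and first dose are both at Visit 2 (Protocol Table 8-1). Never-starters are taken to respond like usual care and starters at the planned inclisiran values. All would give a Day 330 sample if followed.

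**3. Variable 2.** Inclisiran rate if followed: 0.75 × (1 − k/192) + 0.55 × k/192. If lost and set to non-responder: 0.75 × (1 − k/192). The shift is 0.55 × k/192. Usual care is 0.55 in both cases.

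**4. Variable 1.** Difference if followed: 15 × (1 − k/192). If never-starters have no post-baseline value, the MMRM estimates 15. The shift is 15 × k/192.

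| k | Var. 2 difference, followed | Var. 2 difference, lost | Understated by | Odds ratio, followed / lost | Var. 1 difference, followed | Var. 1 difference, lost | Overstated by |
|---|---|---|---|---|---|---|---|
| 0 | 20.0 | 20.0 | 0 | 2.45 / 2.45 | 15.00 | 15 | 0 |
| 2 | 19.8 | 19.2 | 0.6 | 2.43 / 2.36 | 14.84 | 15 | 0.16 |
| 4 | 19.6 | 18.4 | 1.1 | 2.40 / 2.26 | 14.69 | 15 | 0.31 |
| 10 | 19.0 | 16.1 | 2.9 | 2.32 / 2.01 | 14.22 | 15 | 0.78 |

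**5. Scale.** At 192 per arm the standard error is 40 × √(2/192) = 4.1 points for variable 1 and √[(0.55 × 0.45 + 0.75 × 0.25)/192] = 4.8 points for variable 2. At k = 10 the shifts are about 0.2 and 0.6 standard errors. Power for variable 2 at 192 per arm, with no other losses, is then 0.95 if never-starters are followed and 0.85 if they are lost.

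**The case against.** Much of the case on the other side stands.

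- **8.1.1 does not say that follow-up ends.** Study exit is inferred from SAP usage and the glossary. The inference is reasonable but not certain.
- **9.1.1 may already cover a refuser.** Someone who declines the first injection without withdrawing consent arguably falls under its rule to return for assessments where possible. But then 8.1.1 and 9.1.1 give a site different signals, and 8.1.1 is the one that names never-starters.
- **The example suggests a narrow group.** The parenthesis in 8.1.1 resembles the glossary's mis-randomized participants. The sentence itself covers anyone who fails to start.
- **The plan has partial safeguards.** SAP 2.5.6 repeats variable 2 on observed data, and SAP 2.3.1 tabulates early study discontinuation and its reasons by arm. These would expose the loss but not recover the values. At k = 10 the observed-data analysis gives 20.0 points against 19.0 with full follow-up.
- **The fix may recover little.** If those who refuse also withdraw consent, nothing is gained.

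A reader might infer more than the documents support:

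- **That only the inclisiran arm can lose participants.** This rests on a SAP start-date definition, not a site instruction. Randomization in error can occur in either arm, and no passage says that a mis-randomized usual-care participant is kept.
- **That the estimands require these data.** They list discontinuation of study treatment, and the glossary places intercurrent events after treatment initiation. Never starting is not listed. The requirement comes from the Full Analysis Set and the intent-to-treat principle.
- **That a sample drawn days after randomization will enter as the Day 90 result.** SAP Table 2-2 would permit this, since that window opens at study day 1. But 8.1.1 asks for no such sample, and the window applies to early leavers in both arms.

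**Conclusion.** The point holds as an inconsistency that should be removed. 8.1.1 invites sites to end follow-up of participants whom the Full Analysis Set, the SAP's never-dosed provisions and 9.1.1 all keep, and the loss would fall mainly, not exclusively, on the inclisiran arm.

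The size is probably small and may be nil. At an assumed 0 to 10 never-starters of 192, variable 2 is understated by 0 to 2.9 of the planned 20 points and variable 1 overstated by 0 to 0.8 of 15. These figures require that never-starters respond like usual care and would otherwise have given a Day 330 sample. The variable 1 figure also requires that they have no post-baseline LDL-C.

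A reader might infer that 8.1.1 seriously biases both primary results in opposite directions. The documents do not support that: the opposite signs come from the two missing-data rules in SAP 2.5.4, the variable 2 shift is against inclisiran, and both shifts are below one standard error over the assumed range. Required sample size does not change.

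**What to change.** Replace the sentence in Protocol 8.1.1 with one to this effect: randomized participants who receive no study drug, including those randomized in error in either arm, are recorded as not having started study treatment. They remain in the study, attend Visits 3 to 5 with LDL-C unless they withdraw consent, and are analyzed as randomized. Keep the term early terminator for participants who actually leave the study.

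The cost is one amended sentence, a CRF completion note and a few visits that are already scheduled. No endpoint, analysis set, dose rule or sample size changes.
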